- Hair quality assessment including normalization of exclamation point hairs and hair shedding will be described.
- Vellus and Indeterminate scalp hair will be described.
- Non-scalp hair assessments (body and nasal hair) will be described.

Statistical Methods:

Sample Size/ Power Calculations

The planned sample size 80 enrolled is based on an estimated completion rate from study ATI-501-AUAT-201.

Statistical Methods

Subject demographic and baseline characteristics, including medical and alopecia history, prior medications and therapies and physical examination findings will be summarized using descriptive statistics.

Summary descriptive statistics (N, mean, median, SD) by visit will be provided for all safety and efficacy parameters. The Intent to Treat population will be used for all efficacy assessments and the Safety population will be used for all safety assessments. No data imputation will be used.

No inferential analyses are planned. For all efficacy evaluations described below, summary statistics will be provided for all treated subjects pooled, and also for each of two sub-groups of subjects based on the treatment they previously received in study ATI-501-AUAT-201.

Primary Efficacy Analyses

For the primary endpoint, the primary efficacy variable will be the mean relative percent change from the original baseline visit in study ATI-501-AUAT-201 in the SALT score to Visit 6 (Week 24). This represents the percentage of hair regrowth. It will be calculated as the mean of the changes from baseline SALT score to the SALT score at Visit 6 (Week 24), divided by baseline SALT score and expressed as a percentage.

Date: 09NOV2018, Version 1.0 Page 7 of 80 CONFIDENTAL

Secondary Efficacy Analyses

Protocol: ATI-502-AA-203

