The secondary efficacy endpoints will be calculated using both the current study baseline scores and the baseline scores from study ATI-501-AUAT-201. These endpoints will be evaluated at each visit and will include: the mean relative percent change from baseline in the ALODEX score (percent regrowth); the mean change from baseline in SALT and the mean change from baseline in ALODEX, the proportion of subjects achieving a \geq 50% and \geq 75% hair regrowth compared with baseline; change from baseline in the ASAA (Clinician and Subject), PhGIS, AFHA, SGIS, AIA, and treatment satisfaction questionnaires. The mean relative percent change in ALODEX score analysis will use the same methodology as specified for the primary efficacy analysis. Other parameters will be summarized as detailed in the statistical analysis plan.

Safety Data

Safety analyses will include descriptive statistics calculated on the safety parameters using the safety population. The proportion of subjects with treatment-emergent adverse events will be tabulated and presented by Medical Dictionary for Regulatory Activities (MedDRA) System Organ Class. Vital signs and clinically significant abnormal laboratory results will also be tabulated and presented.

Data from enrolled subjects will be presented and summarized. Safety summaries will include listings by study medication of adverse events incidences within each MedDRA System Organ Class, and changes from pre-dose values in vital signs. Adverse event summaries will be presented showing the proportion of subjects experiencing adverse events, both overall and by MedDRA System Organ Class.

Date: 09NOV2018, Version 1.0 Page 8 of 80 CONFIDENTAL

TABLE OF CONTENTS, LIST OF TABLES, AND LIST OF FIGURES

INVEST	GIGATOR'S AGREEMENT	3
SYNOPS	SIS	4
TABLE	OF CONTENTS, LIST OF TABLES, AND LIST OF FIGURES	9
LIST OF	TABLES	13
LIST OF	F ABBREVIATIONS AND DEFINITIONS OF TERMS	14
1.	INTRODUCTION	16
1.1.	Overview of Alopecia Areata	16
1.2.	Immunopathology & Pathophysiology of AA	17
1.3.	Previous Clinical Study Experience with ATI-501	18
1.4.	Clinical Study Experience with ATI-502 Topical Solution	19
1.5.	Study Rationale	19
1.6.	Study ATI-501-AUAT-201	20
2.	TRIAL OBJECTIVES AND ENDPOINTS	21
2.1.	Objectives	21
2.2.	Efficacy Endpoints	21
2.2.1.	Primary Efficacy Endpoint	21
2.2.2.	Secondary Efficacy Endpoints:	21
2.3.	Safety Endpoints	22
2.4.	Other Assessments	22
3.	INVESTIGATIONAL PLAN	23
3.1.	Overall Study Design.	23
3.2.	Number of Subjects	23

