2.3. Safety Endpoints

Safety variables to be assessed include: adverse events, clinical laboratory tests (hematology, clinical chemistry, and urinalysis), vital sign measurements (systolic and diastolic blood pressures, respiration rate, heart rate, and oral or ear body temperature), physical exam, and electrocardiograms.

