3.4. Dose Adjustment Criteria

Subjects should not modify the study medication dosage or frequency without the investigator's prior approval. All study medication modifications must be reported on the appropriate eCRF. If study medication intolerance or safety issue occurs, after consulting with the Aclaris Therapeutics, Inc. Medical Monitor (see page 1), the investigator or designee may direct the subject to modify the study medication frequency from twice-daily to once-a-day. If the subject cannot apply the study medication twice-daily for more than 4 consecutive days, other dose modifications and continuation in the study must be reviewed with the Medical Monitor.

Date: 09NOV2018, Version 1.0 Page 23 of 80 CONFIDENTAL

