3.4.1. Safety Criteria for Adjustment or Stopping Doses

3.4.1.1. Study Medication Interruption

Protocol: ATI-502-AA-203

Treatment with ATI-502 Topical Solution should be temporarily interrupted in the event of severe adverse events considered related to ATI-502, or in the event of one or more of the abnormal laboratory values listed in Table 2.

Table 2: Study Medication Interruption Criteria

Laboratory Test	Hold Study Medication if:	Resume Study Medication if:
WBC count	$< 2 \times 10^{3}/\mu L$	$\geq 2.5 \times 10^{3}/\mu L$
ANC	$< 1 \times 10^{3}/\mu L$	$\geq 1.5 \times 10^{3}/\mu L$
Lymphocyte count	$< 0.5 \times 10^{3}/\mu L$	$\geq 0.75 \times 10^{3}/\mu L$
Platelet count	$< 75 \times 10^3 / \mu L$	Returns to Baseline values
Hemoglobin	< 8 g/dL or a decrease > 2g/dL (from baseline value on ATI- 501-AUAT-201)	$\geq 10 \text{ g/dL}$
AST or ALT	> 3 x ULN	< 2 x ULN or within 20% of Baseline values
Serum creatinine	>2 x ULN	<1.5 x ULN or within 10% of Baseline value

Subjects with one or more of laboratory values meeting the Study Medication Interruption Criteria found in Table 2 must have repeat lab testing performed with results meeting the minimum criteria for resumption in order to initiate treatment

During treatment, if a subject has one or more of the abnormal laboratory values noted in Table 2, the investigator or designee upon receipt and review of the central laboratory report should instruct the subject to hold study medication dosing. The investigator or designee should ask the subject about symptoms, concomitant illnesses and medications and repeat the test(s) as soon as possible. The Medical Monitor must be notified of dose interruptions due to SAEs considered related to study medication or laboratory abnormalities noted in Table 2.

If the retest confirms the abnormal laboratory value, then the study medication should continue to be held followed by repeat testing once a week or sooner at the discretion of the investigator. The subject should be followed until the laboratory abnormality(s) returns to normal or to Baseline (Visit 1) values.

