8.1.5. Clinical Laboratory Assessments

A qualified staff member will collect non-fasting samples for clinical laboratory analysis at the visits detailed in Schedule of Assessments (Table 3). Samples will be sent to a central laboratory for analysis. Refer to the study specific laboratory manual for handling and shipping instructions. The following tests will be conducted:

Chemistry Panel

Albumin

Alkaline phosphatase

Alanine aminotransferase (ALT)

Aspartate aminotransferase (AST)

Blood urea nitrogen (BUN)

Bicarbonate

Calcium

Chloride

Creatinine

Glucose

Lactate dehydrogenase (LDH)

Phosphorus

Potassium

Sodium

Total bilirubin

Total protein

Uric acid

CPK

Crk

Total cholesterol, LDL, HDL,

Triglycerides

Urine Pregnancy Test for WOCBP

(At the visits detailed in Schedule of

Assessments (Table 3)).

Complete Blood Count

Hematocrit

Hemoglobin

Platelet count

Red blood cell morphology

Red blood cell count

White blood cell count

White blood cell differential

% & absolute

Basophils

Eosinophils

Lymphocytes

Monocytes

Neutrophils

Urinalysis

Total cholesterol, LDL, HDL and Triglycerides will be assessed at all visits. The results of the clinical laboratory tests will be reported on the central laboratory's standard reports. The investigator must note NCS or CS to define the clinical relevance of any result that is outside the normal range for the laboratory. The investigator must date and initial every laboratory report.

Date: 09NOV2018, Version 1.0 Page 47 of 80 CONFIDENTAL

The investigator or subinvestigator must review all the laboratory test results against the study entry criteria and the Study Medication Interruption Criteria Table 2 for each subject. Subjects with laboratory values meeting the Study Medication Interruption Criterial found in Table 2 must have repeat laboratory testing performed with results meeting the minimum criteria for resumption.

The investigator must report all laboratory results from samples collected on the ATI-502-AA-203 study that are BOTH outside the normal range for the laboratory AND, in the opinion of the investigator, CS as an AE. Laboratory results from samples collected at V9 on the ATI-501-AUAT-201 study that are BOTH outside the normal range for the laboratory AND, in the opinion of the investigator, CS must be reported as medical history on the ATI-502-AA-203 study eCRF. The investigator must review all laboratory reports in a timely manner.

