9.5. Safety Analyses

Protocol: ATI-502-AA-203

Safety analyses will include descriptive statistics calculated on the safety parameters using the safety population. The proportion of subjects with treatment-emergent adverse events will be tabulated and presented by Medical Dictionary for Regulatory Activities (MedDRA) System Organ Class. Vital signs and clinically significant abnormal laboratory results will also be tabulated.

Data from all enrolled subjects will be presented and summarized. Safety summaries will include listings of adverse events incidences within each MedDRA System Organ Class, and changes from pre-dose values in vital signs. Adverse event summaries will be presented showing the proportion of subjects experiencing adverse events, both overall and by MedDRA System Organ Class.

Date: 09NOV2018, Version 1.0 Page 55 of 80 CONFIDENTAL

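### Beyond by-visit descriptive statistics, laboratory safety is tabulated only through the investigator's clinically significant label, so a value that meets the protocol's own hold rule can appear in no safety count

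*Combined protocol and SAP*

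**What the plan says.** Section 9.5 plans two kinds of laboratory output. The first is general: "Safety analyses will include descriptive statistics calculated on the safety parameters using the safety population". The synopsis (Statistical Methods) is more specific: "Summary descriptive statistics (N, mean, median, SD) by visit will be provided for all safety and efficacy parameters". Section 2.3 counts "clinical laboratory tests (hematology, clinical chemistry, and urinalysis" among the safety variables, so these summaries include the laboratory tests. The second is the tabulation of abnormal results: "Vital signs and clinically significant abnormal laboratory results will also be tabulated". The synopsis (Safety Data) says the same: "Vital signs and clinically significant abnormal laboratory results will also be tabulated and presented". Change from pre-dose is named for vital signs only.

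Section 8.1.5 governs the label: "The investigator must note NCS or CS to define the clinical relevance of any result that is outside the normal range for the laboratory". It requires an adverse event report only when a result is both out of range and, in the investigator's opinion, clinically significant (CS, as opposed to NCS).

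Section 3.4.1.1 (Table 2) gives numeric hold criteria for WBC, ANC, lymphocytes, platelets, hemoglobin, AST/ALT and creatinine. Section 3.4.1.2 gives stop criteria for the same tests. The hemoglobin hold entry is "< 8 g/dL or a decrease > 2g/dL (from baseline value on ATI- 501-AUAT-201"; it carries no normal-range condition. On dose changes, Section 3.4 says: "All study medication modifications must be reported on the appropriate eCRF". Section 9.5 plans no summary of those records.

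**The concern.** The protocol names the laboratory harms it is watching for and gives each a number. The planned tabulation of abnormal results does not use those numbers. It uses a judgement made result by result, by unblinded investigators, at about 25 sites.

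Safety and tolerability come first in the primary objective (Section 2.1), and there is no control arm against which to read a mean. A reader of the study report would want to know how many subjects reached a hold or stop level and how many had drug held. As written, neither number is planned. Drug could be held under the hemoglobin rule while the report shows no clinically significant hemoglobin result and no related adverse event.

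**Working it through.** The plan states no figure to reproduce: N = 80 has no power calculation behind it, and no inferential analysis is planned. The check is a trace of the rules, followed by arithmetic on assumed values.

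**1. Rule trace, hemoglobin.** Take an illustrative baseline of 16.0 g/dL in ATI-501-AUAT-201 and a later value of 13.8 g/dL that is in range.
- Table 2 hold: fall = 16.0 − 13.8 = 2.2 > 2, so the criterion is met.
- CS/NCS label (8.1.5): required only if out of range, so not required.
- Adverse event report (8.1.5): required only if out of range and CS, so not required.
- Tabulation (9.5): takes abnormal CS results, so the value need not enter it.
- By-visit statistics: the value enters the mean, median and SD if it came from a scheduled visit (laboratory tests at Weeks 4, 8, 16, 24 and 28). It is not counted.
- Hold: recorded on the eCRF and notified to the Medical Monitor, but no summary is planned.

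**2. Rule trace, other tests.** The AST/ALT and creatinine criteria are multiples of the upper limit of normal, so values meeting them are out of range by definition. The absolute hematology levels almost certainly are too, although the documents give no reference limits. These values must be labelled, and they drop out of the CS tabulation only if labelled NCS.

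**3. When the in-range hemoglobin route exists.** With 201 baseline B and lower limit of normal LLN, the band of values is LLN ≤ Hb < B − 2, with width max(0, B − 2 − LLN). LLN of 12.0 to 13.5 g/dL is an assumption.

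| B (g/dL) | LLN 12.0 | LLN 13.0 | LLN 13.5 |
|---|---|---|---|
| 14 | 0 | 0 | 0 |
| 15 | 1.0 | 0 | 0 |
| 16 | 2.0 | 1.0 | 0.5 |

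**4. What by-visit means can show.** Assume k of 80 subjects each fall 2.5 g/dL and stay in range. The mean shifts by −2.5k/80.
- k = 4: threshold count 4/80 = 5.0% (exact 95% CI 1.4 to 12.3%); mean shift −0.125 g/dL.
- k = 8: threshold count 8/80 = 10.0% (exact 95% CI 4.4 to 18.8%); mean shift −0.25 g/dL.

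The 95% half-width of a mean change is 1.96 × SD/√80: 0.13 g/dL for an assumed SD of 0.6 and 0.22 g/dL for an SD of 1.0. The shift at k = 4 is inside that noise. At k = 8 it is slightly outside, but a mean still does not say how many subjects were affected. In both cases the CS tabulation could show 0/80.

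**5. Chance that the case arises.** If the true rate of such falls were 1%, 2% or 5% (assumed), the chance of at least one among 80 is 1 − (1 − p)^80 = 55%, 80% or 98%.

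**The case against.** The strongest reply is that the plan reports more than the CS tabulation. By-visit descriptive statistics cover every laboratory parameter, and Section 9.5 says that data from all enrolled subjects will be presented. That stands: a reader might infer that laboratory results without a CS label go unreported, and the documents do not support it. What is missing is a count.

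A reader might also infer that an in-range fall is barred from the CS tabulation and from the adverse event tables. It is not. Section 8.1.5 sets what must be labelled and reported; it does not forbid more. Section 8.2.1.1 allows abnormal laboratory values to describe an adverse event, and Section 3.4.1.1 itself calls Table 2 values abnormal. The fall need not appear; it may.

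Nor does the in-range route extend to all seven tests. It applies only to the hemoglobin-fall criterion, and no stop rule in 3.4.1.2 uses that fall. For the other tests, an investigator would have to call NCS a value that led to a hold and a notice to the Medical Monitor. That is possible, but nothing shows it to be likely.

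It is tempting to add that by-visit means drift toward normal because affected subjects are held until recovery. That is not shown: a triggering value from a scheduled visit still enters that visit's summary.

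Finally, no separate SAP text is available, and one could contain threshold tables. The protocol's deferral to a SAP sits in its efficacy text, however, and Section 9.5 defers no laboratory output. Because central laboratory values are retained, the tables could also be produced later. This limits the harm, but it is not a reason to leave them unplanned.

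**Conclusion.** The point holds in a narrow form. Apart from by-visit descriptive statistics, the only laboratory tabulation shown is of abnormal results that the investigator labels clinically significant. No count against the Table 2 or 3.4.1.2 thresholds, no laboratory change from baseline and no summary of interruptions is planned in the documents. An in-range hemoglobin fall of more than 2 g/dL can trigger a hold and appear in no safety count.

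The size is unknown. Reference limits, baselines, SDs, fall sizes and event counts above are all assumptions, and the in-range band vanishes at a baseline of 14 g/dL for every LLN tried. The scenarios show what could be hidden, not what is expected. This is a cheap improvement to reporting in an uncontrolled study. It is not a flaw in the design or in the data collected.

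A separate inconsistency came up in the trace. In the Table 2 hemoglobin row, one value can meet both the hold entry (a fall of more than 2 g/dL) and the resume entry (at least 10 g/dL); the 13.8 g/dL example does. The sponsor must reconcile these entries. Nothing here says which is right.

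**What to change.** In Section 9.5 and the synopsis, keep the CS tabulation and add the following, all in the Safety population:

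- **(a) Hold criteria.** Number and percentage of subjects with at least one post-first-dose central laboratory value, scheduled or unscheduled, meeting each Table 2 hold criterion, regardless of the CS/NCS label. Compute the hemoglobin fall from the ATI-501-AUAT-201 baseline. The documents describe transfer of Visit 9 assessments but do not say that the 201 baseline laboratory values are carried over, so import that value if it is not already in the dataset.
- **(b) Stop criteria.** The same count for the single-value numeric levels in 3.4.1.2. Derive the second-occurrence, persistence, retest-confirmed and combined AST/ALT with bilirubin or symptom criteria from each subject's full sequence of results and records. A worst value per subject cannot identify them.
- **(c) Change.** Change from the last pre-dose value for these tests.
- **(d) Drug modification.** Number and percentage of subjects with study medication held, reduced in frequency or permanently discontinued, with reason, from the eCRF.

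The cost is some wording, two or three extra tables, and possibly the import of one baseline value per subject. The reported frequency of laboratory abnormalities may look less favourable. No threshold or treatment rule changes.

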10. TRAINING, DATA HANDLING AND RECORD KEEPING

10.1. Training

Protocol: ATI-502-AA-203

For each investigational center, participants will be trained to the protocol, study specific procedures, and the eCRFs. Those unable to attend the training must receive on-site training from an appropriately trained individual prior to participating in any of the procedures and evaluations in this study.

Clinical Research Associates (CRAs) and other applicable personnel will be trained prior to study initiation to familiarize CRAs with the disease, the Standard Operating Procedures (SOPs), the protocol and other study specific items. Team organization, communication and operational issues will also be discussed.

Aclaris Therapeutics, Inc. or designee will provide an investigational center file to each center.

10.2. Data Collection

The Investigator must maintain required records for all study subjects. Data for this study will be recorded in the subject's source document and on the eCRFs. All data on these eCRFs should be recorded completely and promptly. A copy of the completed eCRFs for each subject will be retained by the investigational center.

Records of the subject's participation in this study will be held confidential except as disclosure is required by law. The study doctor, the sponsor, persons working on behalf of the sponsor, and under certain circumstances, the United States Food and Drug Administration and the Institutional Review Board will be able to inspect and copy confidential study-related records that identify subjects by name. Therefore, absolute subject confidentiality cannot be guaranteed. If the results of this study are published or presented at meetings, the subject's identity will not be revealed.

10.3. Data Management

Data-management activities of this study will be subcontracted. Edit checks and review processes will be performed by the sub-contractor until all data clarifications are resolved. The data will be exported to be stored in SAS datasets (or equivalent) by the sub-contractor. After all data clarifications are resolved and subject's evaluability is determined, the database will be locked.

10.4. Study Monitoring

During the study, a monitor from Aclaris Therapeutics, Inc. or representative will have regular contacts with the investigational site, for the following:

- Provide information and support to the investigator(s)
- Confirm that facilities remain acceptable

Date: 09NOV2018, Version 1.0 Page 56 of 80 CONFIDENTAL

• Confirm that the investigational team is adhering to the protocol, that data are being accurately recorded in the case report forms, and that investigational product accountability checks are being performed

- Perform source data verification. This includes a comparison of the data in the case report forms with the patient's medical records at the hospital or practice, and other records relevant to the study. This will require direct access to all original records for each patient (e.g. clinic charts).
- Record and report any protocol deviations not previously sent to Aclaris Therapeutics,
 Inc.
- Confirm AEs and SAEs have been properly documented on CRFs and confirm any SAEs have been forwarded to Aclaris Therapeutics, Inc. and those SAEs that met criteria for reporting have been forwarded to the IRB.

The monitor will be available between visits if the investigator(s) or other staff needs information or advice.

10.5. Source Documentation

Protocol: ATI-502-AA-203

Investigators must keep accurate separate records (other than the eCRFs) of all subjects' visits that include all pertinent study related information. A statement should be made indicating that the subjects have been enrolled in this clinical study and have provided written informed consent. Any AEs must be completely documented. Source documentation includes results of any diagnostic tests conducted during the study.

